### **7.2 Justification for Exclusions**

Pregnant women are excluded from this study because the effects of AZD6244 on the developing fetus is unknown and because radiation is a known teratogen. Because there is an unknown but potential risk for adverse events in nursing infants secondary to treatment of the mother with AZD6244, breastfeeding should be discontinued if the mother is treated with AZD6244. Participants with unstable or serious medical conditions such as uncontrolled diabetes, uncontrolled hypertension, symptomatic congestive heart failure, unstable angina pectoris, myocardial infarction within the past 6 months, uncontrolled cardiac arrhythmia; or psychiatric illness/social situations that would limit compliance with study requirements are excluded due to the possibility that the underlying condition may obscure the attribution of effect and adverse events and may limit study compliance. HIV-positive patients on combination antiretroviral therapy are ineligible because of the potential for pharmacokinetic interactions with AZD6244. Appropriate studies will be undertaken in patients receiving combination antiretroviral therapy when indicated.

### **7.3 Participation of Children**

This study includes patients 18 years of age and older. Because insufficient dosing or adverse event data are currently available on the use of AZD6244 in patients <18 years of age, children are excluded from this study, but may be eligible for future pediatric trials. Studies will be performed in patients <18 years of age when it is appropriate to do so.

### **7.4 Evaluation of Benefits and Risks/Discomforts**

There may or may not be any clinical benefit to a patient from participation in this trial. Their participation will benefit future cancer patients. Potential risks include the possible occurrence of any of a range of side effects that are listed in the consent document. It is possible that the side effects of radiation treatment and Capecitabine may be increased with AZD6244. The procedure for protecting against or minimizing risks will be to exclude patients with known contraindications to this therapy and to medically evaluate patients as described in protocol Section 3.3. Although no compensation is available, any injury will be fully evaluated and treated in keeping with the benefits or care to which participants are entitled under applicable regulations.

Optional biopsies will be obtained during sigmoidoscopy. The risks of sigmoidoscopy include discomfort during the procedure, bleeding, infection, gas, and the remote risk of perforation.

### **7.5 Consent and Assent Process and Documentation**

An associate or principal investigator on the trial will inform patients of the purpose, alternatives, drug administration plan, research objectives and follow-up of this trial. The patient will be provided an IRB-approved consent for review and signature and his/her questions will be answered. After a decision is made to enroll into the study, a signature will be obtained from the patient. The original signed consent goes to Medical Records; a copy will be placed in the research record. All patients must have a signed informed consent form and an on-study (confirmation of eligibility) form filled out and signed by a participating investigator before entering on study.

### **7.6 Procedure for Protecting Against or Minimizing Any Potential Risks**

All care will be taken to minimize side effects, but they can be unpredictable in nature and severity. This study may involve risks to patients, which are currently unforeseeable. All patients will be monitored for side effects from taking study medication. This research represents a greater than minimal risk to participants, but presents the prospect of direct benefit to individual subjects.

#### 7.6.1 Patient Advocate

The patients' rights representative is available to patients receiving treatment on this protocol at the NIH Clinical Center at [contact] in Building 10 of the Clinical Research Center, Room 1-3521, on the Bethesda NIH campus. Patients will be informed that they can contact the study PI or RN at any time with questions about their medical care, and that the patients' rights representative is also available to answer nonmedical questions about the study.

### **8. PHARMACEUTICAL INFORMATION**

A list of the adverse events and potential risks associated with the investigational or commercial agents administered in this study can be found in Section 6.1.

#### **8.1 CTEP-Supplied Investigational Agent(s)**

##### 8.1.1 AZD6244 Hydrogen Sulfate (NSC 748727)

- **Chemical Name:** 6-(4-Bromo-2-chloro-phenylamino)-7-fluoro-3-methyl-3H-benzimidazole-5-carboxylic acid (2-hydroxy-ethoxy)-amide hydrogen sulfate
- **Other Names:** ARRY-142886; AR00142866; AR-142886-01
- **Classification:** Mitogen-activated protein kinase (MEK) inhibitor
- **CAS Registry Number:** 943332-08-9
- **Molecular Formula:** C17H15BrClFN4O3 · H2SO4
- **M.W.:** 555.7
- **Solubility:** Solubility in Captisol® approximately 1 mg/mL at 25°C. Very low aqueous solubility (3.4 mcg/mL at pH 7.4).
- **Mode of Action:** The RAS/RAF/MEK/ERK pathway is an important mediator of many cellular processes including proliferation, survival, differentiation, apoptosis, motility, and metabolism. This pathway is often aberrantly activated in human tumors due to the overexpression of activated K-RAS, mutant b-Raf, or other growth factor receptors. AZD6244 is a selective mitogen-activated protein kinase (MEK) inhibitor. By inhibiting MEK, AZD6244 inhibits ERK phosphorylation. Thus, AZD6244 may inhibit oncogenic growth signaling in tumor cells by targeting the RAS/RAF/MEK/ERK pathway.
- **How Supplied:** AZD6244 hydrogen sulfate is supplied as a 25 mg, size 4, plain, white, hydroxypropylmethylcellulose (HPMC) capsule in white high density polyethylene (HDPE) containers with foil-lined, induction-sealed, child-resistant closures. Each bottle contains 60 capsules. Each capsule contains a dispersion of AZD6244 hydrogen sulfate in d- $\alpha$ -tocopheryl polyethylene glycol 1000 succinate (TPGS; a water soluble form of vitamin E).
- **Storage:** Store the AZD6244 hydrogen sulfate capsules at room temperature (20°C-25°C). Brief excursions are permitted between 15°C and 30°C.
- **Stability:** Stability studies are ongoing.
- **Route of Administration:** Oral. Take AZD6244 capsules on an empty stomach

(either 1 hour before or 2 hours after meals). AZD6244 capsules should be taken with water only.

- **Potential Drug Interactions:** AZD6244 is primarily metabolized by CYP1A2 to N-desmethyl AZD6244 which is 3-5 fold more pharmacologically active than AZD6244.

*In vitro*, AZD6244 is metabolized to a lesser extent by CYP2C19 and CYP3A4.

*In vitro*, AZD6244 is a weak inhibitor of CYP2C9 and CYP1A2.

High vitamin E doses may potentiate warfarin's anticoagulant activity. Monitor PT/INR more frequently in patients receiving both warfarin and AZD6244 hydrogen sulfate capsules. Avoid concomitant intake of Vitamin E in excess of 100% of the recommended daily dose.

### 8.1.2 Agent Ordering

AZD6244 (NSC 748727) may be requested by the Principal Investigator (or their authorized designee) at each participating institution. Pharmaceutical Management Branch (PMB) policy requires that agent be shipped directly to the institution where the patient is to be treated. PMB does not permit the transfer of agents between institutions (unless prior approval from PMB is obtained.) The CTEP-assigned protocol number must be used for ordering all CTEP-supplied investigational agents. The responsible investigator at each participating institution must be registered with CTEP, DCTD through an annual submission of FDA form 1572 (Statement of Investigator), Curriculum Vitae, Supplemental Investigator Data Form (IDF), and Financial Disclosure Form (FDF). If there are several participating investigators at one institution, CTEP-supplied investigational agents for the study should be ordered under the name of one lead investigator at that institution.

Agent may be requested by completing a Clinical Drug Request (NIH986) and faxing it to the Pharmaceutical Management Branch at [contact]. For questions about drug orders, transfers, returns, or accountability call [contact] Monday through Friday between \*:30 am and 4:30 pm (ET) or email [[contact]](mailto:[contact]) anytime.

### 8.1.3 Agent Accountability

Agent Inventory Records – The investigator, or a responsible party designated by the investigator, must maintain a careful record of the inventory and disposition of all agents received from DCTD using the NCI Drug Accountability Record Form (DARF). (See the CTEP home page at <http://ctep.cancer.gov> for the Procedures for Drug Accountability and Storage and to obtain a copy of the DARF and Clinical Drug Request form.)

## 8.2 **Commercial Agent(s):**

### 8.2.1 Capecitabine

**Chemical Name:** 5'-deoxy-5-fluoro-N-[(pentyloxy) carbonyl]-cytidine

**Other Names:** xeloda

**Classification:** Fluoropyrimidine carbamate

**M.W.:** 359.35

**Solubility:** Aqueous solubility of 26 mg/mL at 20°C.

**Mode of Action:** Capecitabine is readily absorbed in the gastrointestinal tract and hydrolyzed in the liver to 5'-deoxy-5-fluorocytadine (5'-DFCR). Cytidine deaminase converts 5'-DFCR to 5'-deoxy-5-fluorodine (5'-DFUR) which is further hydrolyzed to the active drug 5-FU. 5-FU is metabolized to 5-fluoro-2'-deoxyuridine monophosphate (FdUMP) and 5-fluorouridine triphosphate (FUTP). FdUMP binds covalently to thymidylate synthase and thereby inhibits the formation of thymidylate from 2'-deoxyuridylate. Thymidylate is the necessary precursor of thymidine triphosphate, which is essential for the synthesis of DNA, so that a deficiency of this compound can inhibit cell division. Nuclear enzymes can mistakenly incorporate FUTP in place of uridine triphosphate during synthesis of RNA which can interfere with RNA processing and protein synthesis.

**How Supplied:** Capecitabine is supplied as a biconvex oblong film coated caplet containing either 150 mg of capecitabine or 500 mg of capecitabine. The inactive ingredients in capecitabine include anhydrous lactose, croscarmellose sodium, hydroxypropyl methylcellulose, microcrystalline cellulose, magnesium stearate, and purified water. The film coating contains hydroxypropyl cellulose, talc, titanium dioxide, and synthetic yellow and red iron oxides.

**Storage:** Store at 25° C; excursions permitted to 15 to 30° C.

**Route of Administration:** Oral.

**Potential Drug Interactions:** Administration with Warfarin can increase the INR beyond expected. Capecitabine should not be administered with aluminum hydroxide or magnesium hydroxide containing antacids, such as Maalox, as it may increase the plasma concentrations of capecitabine and its metabolites.

**Source:** Capecitabine will be purchased from commercial sources by the NIH Clinical Center Pharmacy Department.

**Note:** The reader is referred to the capecitabine package insert for additional information.

## 9. CORRELATIVE/SPECIAL STUDIES

### 9.1 Laboratory Correlative Studies

#### 9.1.1 Tumor Biopsies

##### 9.1.1.1 Tumor mutational status – Laboratory Correlative Study #1

- Collection of specimens: Biopsy specimen will be obtained at the time of pretreatment endoscopy. If sufficient tissue is available for this study from the initial diagnostic biopsy, this biopsy will not be performed.
- Handling of Specimens: biopsies will be collected, immediately placed in sterile saline on wet ice, and transported to the laboratory of [name]. Specimens will be centrifuged to remove supernatant and frozen at -80 C until use.

##### 9.1.1.2 Tumor ERK1/2 phosphorylation – Laboratory Correlative Study #2

- Collection of Specimen: Specimen will be collected at the time of pretreatment endoscopy and on day 8 and day 15. If sufficient tissue is available for this study from the initial diagnostic biopsy, the pretreatment biopsy will not be performed

- Handling of Specimens: The specimen will be submitted to pathology in formalin for processing and immunohistochemistry.

### 9.1.2 Research Labs

#### 9.1.2.1 Peripheral mononuclear cell ERK1/2 phosphorylation – Laboratory Correlative Study #3)

- Collection of Specimen: A whole blood specimen will be collected pretreatment, day 8, day 15, and at four weeks of follow up (week 11). Nurses at the Radiation Oncology clinic will collect whole blood in one 10 cc EDTA tube.
- Handling of Specimens: Whole blood will be collected and transported immediately to the laboratory of [name] for processing for flow cytometric analysis.

#### 9.1.2.2 Plasma TGF $\alpha$ – Laboratory Correlative Study #4)

- Collection of Specimen: Specimen will be collected pretreatment, day 8, day 15, and at four weeks of follow up (week 11). Nurses at the Radiation Oncology clinic will collect whole blood in one 10 cc EDTA tube for plasma.
- Handling of Specimens: Blood for plasma will be immediately transported on ice to the laboratory of [name]. Plasma will be processed within 15 minutes of collection. Aliquots will be stored at -80 C until use.

## 9.2 Sample processing

Biospecimens will be collected and processed using validated SOPs that will ensure both specimen quality and patient confidentiality pursuant to informed consent provisions.

Using a computerized inventory system and a backup hardcopy process, all specimen collection and processing steps will be documented and the specific location of each specimen will be tracked. Each new specimen collected will be assigned a unique barcode identifier that can be linked to the original specimen collected and other relevant information within the inventory system. To ensure patient confidentiality, only containers used for the initial specimen collections will be labeled with patient identifiers. Only the barcode identifier will be applied to all subsequent specimen containers. When specimens are processed and aliquoted, no patient information will be included on the new containers. Original specimen containers will be discarded. Only barcode-labeled specimens without patient identifiers will be sent for analysis and/or storage. Specimen labels will indicate: protocol number, order in which the patient enrolled on the trial, type of sample, collection time, and total volume collected, as appropriate. Samples from sets of at least three patients will be grouped for scientific analysis.

The inventory process contains other security provisions sufficient to safeguard patient privacy and confidentiality. Access to the inventory system and associated documents will be restricted to appropriate individuals. Requests to use specimens stored in the repository must be approved. The only patient information available in the inventory system will be the patient sex, diagnosis, and level of informed consent given. SOPs ensure that any changes in informed consent made by a patient and relayed to the PI will be reflected in the inventory

system to ensure that specimens are destroyed as appropriate. All laboratory personnel will be trained to adhere to SOPs and will be monitored for high-quality performance.

Following completion of this study, samples will remain in storage as detailed above. Access to these samples will only be granted following IRB approval of an additional protocol, granting the rights to use the material.

If, at any time, a patient withdraws from the study and does not wish for their existing samples to be utilized, the individual must provide a written request. Following receipt of this request, the samples will be destroyed (or returned to the patient, if so requested), and reported as such to the IRB. Any samples lost (in transit or by a researcher) or destroyed due to unknown sample integrity (i.e., broken freezer allows for extensive sample thawing, etc.) will be reported as such to the IRB.

Any new use of these samples will require prospective IRB review and approval; any loss or destruction of samples and the planned disposition of samples after the protocol is terminated will be reported to the IRB.

All specimens obtained in the protocol are used as defined in the protocol. Any specimens that are remaining at the completion of the protocol will be stored in the conditions described below. The study will remain open so long as sample or data analysis continues. Samples from consenting subjects will be stored until they are no longer of scientific value or if a subject withdraws consent for their continued use, at which time they will be destroyed. The PI will report any loss or destruction of samples to the NCI IRB as soon as he is made aware of such loss.

If the patient withdraws consent the participants data will be excluded from future distributions, but data that have already been distributed for approved research use will not be able to be retrieved.

The PI will report destroyed samples to the IRB if samples become unsalvageable because of environmental factors (ex. broken freezer or lack of dry ice in a shipping container) or if a patient withdraws consent. Samples will also be reported as lost if they are lost in transit between facilities or misplaced by a researcher. Freezer problems, lost samples or other problems associated with samples will also be reported to the IRB, the NCI Clinical Director, and the office of the CCR, NCI.

## 10. STUDY CALENDAR

Baseline evaluations are to be conducted within 1 week prior to start of protocol therapy. Scans and x-rays must be done  $\leq 4$  weeks prior to the start of therapy.

	Pre-Study	Wk 1	Wk 2	Wk 3	Wk 4	Wk 5	Wk 6	Wk 7	Wk 8	Wk 9	Wk h 11	Follow up 3, 6, 9, 12, 24, and 36 months after completion of chemoradiation
AZD6244		A	A	A	A	A	A	A				

Capecitabine			B	B	B	B	B	B				
Radiation			C	C	C	C	C	C				
Informed consent	X											
Ophthalmologic examination e	X f											
Surgical Consult	X g											
Demographics	X											
Medical history	X											
Concurrent meds	X	X	X	X	X	X	X	X			X	X
Physical exam	X	X	X	X	X	X	X	X			X	X
Vital signs with pulse oximetry	X	X	X	X	X	X	X	X			X	
Height	X											
Weight	X										X	X
Performance status	X											
CBC w/diff, plts, PT/PTT	X	X	X	X	X	X	X	X	X	X	X	X
Serum chemistry a	X	X	X	X	X	X	X	X	X	X	X	X
EKG	X	X h	X i		X i							
Adverse event evaluation	X	X	X	X	X	X	X	X	X	X	X	X g
Tumor measurements	X										X	
Radiologic evaluation	X										X	X
Pathology	X											
CT (CAP)	X										X	X
CEA	X											
Endoscopy	X											
B-HCG	X b											
Optional tumor biopsy	X d		X	X								
PKs		X	X									
Research blood draw	X		X	X							X	

A: AZD6244: Dose as assigned; po BID daily B: Capecitabine, Dose 825 mg/m^2 po every 12 hours, Monday- Friday (2 hours prior to radiation and 12 hours after first dose)

C Radiotherapy: daily Monday- Friday

a Albumin, alkaline phosphatase, total bilirubin, bicarbonate, BUN, calcium, chloride, creatinine, glucose, LDH, phosphorus, potassium, total protein, SGOT [AST], SGPT [ALT], sodium.

b: Serum pregnancy test (women of childbearing potential).

c: Off-study evaluation.

d: If sufficient tissue is available for pretreatment correlative work from the initial diagnostic biopsy this procedure will not be performed.

e. Ophthalmologic evaluation will be repeated in the event of any visual change or visual event due to AZD6244.

f. Baseline ophthalmologic and surgical consultation should be obtained within 3 weeks of beginning protocol therapy.

g. RTOG scoring only

h. Week 11 is pre- surgery

i. EKG will be obtained on Day 1 (2 hours after first AZD6244 dose), Day 8, week 4 and in the case of a cardiorespiratory AE.

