#### 2.1.2.1 Pharmacokinetics

N-desmethyl is the active metabolite of AZD6244, which is 3 to 5 times more potent to the parent compound. An amide metabolite can also be detected in human plasma but is 40 to 50 fold less active than AZD6244. Single dose pharmacokinetics of AZD6244 and N-desmethyl have been characterized following dosing of both the free base suspension (study ARRY-0401) for dose levels between 50 to 300 mg and the

Hyd-Sulfate preparation (D1532C00005) for dose levels between 25 to 100 mg. The parameters described below are those obtained with the Hyd-Sulfate preparation. AZD6244 was absorbed relatively quickly across dose levels, with a median  $t_{max}$  of 1.5 hours. Plasma N-desmethyl AZD6244 concentrations/exposure followed a similar pattern to AZD6244 over time, although  $C_{max}$  and AUC values were <15% of the parent within each patient. Following the peak, AZD6244 concentrations decreased multi-exponentially with a mean half-life ( $t_{1/2}$ ) of 5 to 7 hours. The  $t_{1/2}$  of the N-desmethyl metabolite was 9 to 13 hours. Limited data is available for AZD6244 amide. Concentrations of this metabolite were variable within subjects and between subjects. The time to maximum concentration was highly variable among patients.

Study D1532C00020 evaluated the pharmacokinetics of AZD6244 in patients under fasting conditions and after a high fat meal. Geometric mean  $C_{max}$  and AUC were reduced by approximately 60% and 20% under fed conditions compared to exposure following AZD6244 taken fasted. There was a trend toward a later  $t_{max}$  in the fed condition. Based on these findings it is recommended that AZD6244 should be taken on an empty stomach.

Plasma pharmacokinetic parameters were similar for single and a multiple dosing (day 8, 15, and 22), suggesting minimal accumulation over time with twice daily dosing, consistent with the terminal half-life observed. A similar pharmacokinetic profile was observed on day 8 compared to day 1 supporting that the steady state was achieved in this time. The exposure of AZD6244 N-desmethyl followed a similar pattern. Exposure on multiple dosing was comparable within patients. Comparison of data from 7 or 14 days BID dosing suggest steady state was achieved by day 7.

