Adverse events of fatigue are reported across all studies with AZD6244. In the majority of cases the causality was split approximately equally between study drug and the disease under study. A higher frequency of fatigue AEs were reported with the Hyd-Sulfate preparation compared to the free-base suspension in Phase II monotherapy trials (67.9% vs 20.8%). A minority of fatigue events were CTCAE grade 3 with the highest frequency of 14% of patients in study D1532C0005 including 1 DLT.

Edema (primarily peripheral and periorbital) and fluid accumulation has been reported consistently in studies of AZD6244 with peripheral edema being most common. The underlying etiology of the edema and fluid accumulation adverse events is unclear at present. There is currently no evidence to suggest that the edema is due to congestive cardiac failure. Most peripheral edema AEs were CTCAE grade 1. The time of onset was commonly several weeks into treatment with AZD6244. Some patients required initiation of diuretic therapy to control the peripheral edema.

Some patients receiving AZD6244 have been observed to develop asymptomatic decreases in LVEF in the absence of obvious confounding comorbidities. The co-administration of AZD6244 with other anti-cancer agents, some of which are known to be associated with cardiotoxicity, may be associated with an increased risk of impairment of cardiac function. There have been four AE reports of left ventricular dysfunction, two reports of ejection fraction decreased, and one report each of ventricular dysfunction and ventricular hypokinesia in patients receiving AZD6244 free-base. Two events of left ventricular dysfunction were considered SAEs. In study D153200005 with the Hyd-Sulfate preparation LVEF was monitored and data indicate a trend toward a drop in LVEF across all dose cohorts by week 8 assessments. No comparator data is available and the study population included patients who may have received prior cardiotoxic chemotherapy.

Adverse events of dyspnea have been reported across trials of AZD6244.

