## **4. TREATMENT PLAN**

### **4.1 Protocol Therapy Administration**

#### 4.1.1 AZD6244 administration

Treatment will be administered on an outpatient basis. Reported adverse events and potential risks for AZD6244, radiation, and Capecitabine are described in Section 6. Appropriate dose modifications for AZD6244 and Capecitabine are described in Section 5. No investigational or commercial agents or therapies other than those described below may be administered with the intent to treat the patient's malignancy.

Dose Escalation Schedule			
Dose Level	Dose		
	AZD6244	Capecitabine	Radiation*
Level -1	50 mg PO QD Weeks 1-7	825 mg/m  PO every 12 hours Weeks 2-7	5040 cGy Weeks 2-7
Level 1	50 mg PO BID Weeks 1-7	825 mg/m  PO e every 12 hours Weeks 2-7	5040 cGy Weeks 2-7
Level 2	75 mg PO BID Weeks 1-7	825 mg/m  PO every 12 hours Weeks 2-7	5040 cGy Weeks 2-7

\* An additional 360 cGy may be delivered for fixed T4 tumors for a total dose of 5400 cGy

Dose-escalation of AZD6244 will begin at dose level 1, 50 mg PO BID delivered continuously, 7 days per week beginning one week prior to the initiation of chemoradiotherapy and continuing until the last day of chemoradiotherapy. Dose level -1 will only be delivered if Dose Level 1 is considered to be not tolerated due to toxicity observed in dose level 1 patients.

- Patients will be provided with a Medication Diary for AZD6244 (Appendix D), instructed in its use, and asked to bring the diary with them to each appointment.
- Take AZD6244 capsules on an empty stomach (either 1 hour before or 2 hours after meals). AZD6244 capsules should be taken with water only.
- In the event of AZD6244 de-escalation to dose level -1 (50 mg PO QD), the patient will be instructed to take AZD6244 as a morning dose.
- Follow up for certain adverse events (AEs) should be performed to better characterize the effects of AZD6244 therapy:
  - Patients experiencing **edema** should have cardiac ejection fraction (EF) measurements, electrocardiogram, serum chemistry (including electrolytes and albumin), and routine urinalysis.
  - Patients with symptoms consistent with **cardiac** impairment (*e.g.*, congestive cardiac failure, edema, or dyspnea) should have EF measurements (MUGA scan or echocardiography) and electrocardiogram at the time of the event as well as other routine investigations.

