Edema limbs			Edema limbs (Gr 2)
Fatigue			Fatigue (Gr 2)
	Fever		Fever (Gr 2)
INVESTIGATIONS			
	Alanine aminotransferase increased		Alanine aminotransferase increased (Gr 3)
	Alkaline phosphatase increased		
	Aspartate aminotransferase increased		Aspartate aminotransferase increased (Gr 3)
	Platelet count decreased		
METABOLISM AND NUTRITION DISORDERS			
	Anorexia		Anorexia (Gr 2)
	Hypoalbuminemia		
	Hypomagnesemia		

NERVOUS SYSTEM DISORDERS			
	Dizziness		
	Headache		Headache (Gr 2)
PSYCHIATRIC DISORDERS			
	Insomnia		
RESPIRATORY, THORACIC AND MEDIASTINAL DISORDERS			
	Cough		Cough (Gr 2)
	Dyspnea		Dyspnea (Gr 2)
SKIN AND SUBCUTANEOUS TISSUE DISORDERS			
	Dry skin		Dry skin (Gr 2)
	Pruritus		
	Rash acneiform		Rash acneiform (Gr 3)
	Rash maculo-papular		Rash maculo-papular (Gr 2)
VASCULAR DISORDERS			
	Hypertension		

This table will be updated as the toxicity profile of the agent is revised. Updates will be distributed to all Principal Investigators at the time of revision. The current version can be obtained by contacting [[contact]](mailto:[contact]). Your name, the name of the investigator, the protocol and the agent should be included in the e-mail.

Febrile neutropenia/neutropenic infection has been observed primarily in trials combining Selumetinib (AZD6244) and docetaxel.

SBE-CD (Captisol®, vehicle) in the mix and drink formulation is known to cause soft stools and/or diarrhea in rats and dogs; however, it is possible that some of these findings might be related to exacerbation of the vehicle effect by Selumetinib (AZD6244).

Infection includes all 75 sites of infection under the INFECTIONS AND INFESTATIONS SOC.

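### Cardiac monitoring is not designed to find some effects the protocol names: LVEF is event-driven after screening, the steady-state EKGs are not timed to the dose, and magnesium is not in the scheduled panel

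*Combined protocol and SAP*

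**What the plan says.** **LVEF.** Section 3.3.1 requires an echocardiogram or MUGA at screening. The Section 10 calendar has no ejection-fraction row. Section 4.1.1 repeats the measurement after edema, after a respiratory event, and in patients with symptoms of cardiac impairment, who "should have EF measurements (MUGA scan or echocardiography) and electrocardiogram at the time of the event". Section 2.1.2.2 gives the background: "Some patients receiving AZD6244 have been observed to develop asymptomatic decreases in LVEF in the absence of obvious confounding comorbidities". In a separate sentence, about the study of the Hyd-Sulfate preparation, it says that "LVEF was monitored and data indicate a trend toward a drop in LVEF across all dose cohorts by week 8 assessments". It adds that this study had no comparator and that some patients may have had cardiotoxic chemotherapy before.

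**EKG.** The calendar schedules a pre-study tracing and three on treatment; footnote i reads: "EKG will be obtained on Day 1 (2 hours after first AZD6244 dose), Day 8, week 4 and in the case of a cardiorespiratory AE". Section 2.1.2.1 gives a median tmax of 1.5 h and a mean half-life of 5 to 7 h, and says that data from 7 or 14 days of twice-daily dosing "suggest steady state was achieved by day 7". QT risk drives exclusions 3.2.7 and 3.2.8 and Appendix C. Section 6.2.1.1 lists QTc prolongation among reported events whose relationship is undetermined.

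**Magnesium.** Section 6.2.1.1 lists "Hypomagnesemia" among possibly related events in the less-likely column (up to 20%) and diarrhea in the likely column (over 20%). Footnote a of Section 10 names 16 analytes, among them "glucose, LDH, phosphorus, potassium, total protein". Magnesium is not one of them.

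**The concern.** Section 1.1 makes the toxicity profile a primary objective, so a monitoring schedule also determines what the trial may report. Three features of this one do not match the effects that the protocol itself names. A measurement made only after an event is a weak instrument for a change described as asymptomatic. A 2 h time point was chosen for the first-dose EKG, yet the steady-state tracings have no time point, so a change from Day 1 to Day 8 or week 4 mixes any drug effect with a difference in sampling time. An electrolyte disturbance listed as possibly related, in a regimen where diarrhea is expected, is not in the routine chemistry.

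What is at stake is how absence is read. A final report showing no LVEF decrease or no hypomagnesemia could be taken as evidence of safety when the measurement was not routinely made.

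**Working it through.** The plan gives no sample size, detection probability or error rate for cardiac monitoring, so there is no stated figure to reproduce. The check sets the schedule against the protocol's own background data.

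**1. LVEF.** Scheduled values after screening: 0. All later values depend on a trigger event.

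Let p be the proportion of patients with an LVEF fall and e the probability that an affected patient has a trigger event while the fall is present. The plan's yield then estimates p × e, not p. For example, falls found in 5% of patients would fit p = 0.05/0.20 = 25% or p = 0.05/0.50 = 10%, and nothing in the plan separates these.

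The documents give neither p nor e. As an illustration, take n = 12 (the number at the MTD in Section 13.3), p of 3%, 10% or 20%, and e of 20% to 50%, with e assumed unrelated to the fall:

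| Assumed p | At least one affected, 1 − (1 − p)^12 | At least one found, 1 − (1 − pe)^12, e = 0.2 to 0.5 |
|---|---|---|
| 3% | 31% | 7% to 17% |
| 10% | 72% | 22% to 46% |
| 20% | 93% | 39% to 72% |

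If falls tend to come with edema or dyspnea, e is higher and detection is better than shown.

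**2. EKG.** Inputs from Section 2.1.2.1: tmax 1.5 h, half-life h of 5 to 7 h, steady state by day 7. One-phase approximation: the fraction of peak at time t is 2^(−(t − 1.5)/h).

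- Day 1 tracing at 2 h: 2^(−0.5/5) = 0.93; 2^(−0.5/7) = 0.95.
- Tracing at 12 h, just before a twice-daily dose: 2^(−10.5/5) = 0.23; 2^(−10.5/7) = 0.35.
- 12 h relative to 2 h: 2^(−10/5) = 0.25; 2^(−10/7) = 0.37.
- 24 h relative to 2 h (once-daily level −1): 2^(−22/5) = 0.05; 2^(−22/7) = 0.11.

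Day 1 is thus close to peak after a single dose. A Day 8 or week 4 tracing could lie anywhere from near peak down to about a quarter to a third of it on twice-daily dosing, and footnote i does not require the time from dose to be recorded.

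**3. Magnesium.** Chemistry is drawn in each of weeks 1 to 9 and at week 11, which is 9 + 1 = 10 draws from the start of treatment to the pre-surgery visit, besides the pre-study sample. Scheduled magnesium values: 0. The screening laboratory list in Section 3.3.3 does not name it either. The edema work-up in Section 4.1.1 asks for electrolytes without saying which.

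**The case against.** The monitoring is not empty. Edema alone triggers both an ejection fraction and an EKG, and limb edema is in the over-20% column of Section 6.2.1.1. Respiratory events trigger both as well. EKGs are scheduled on Day 8 and in week 4; they are untimed, not absent. A reader might infer that the plan is blind to cardiac effects. The triggers and scheduled tracings rule that out, and this part of the objection stands.

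A reader might also join the two LVEF statements in Section 2.1.2.2 and infer that the week 8 falls were silent. The text does not say so. The same section records two left ventricular dysfunction events as SAEs, and the week 8 trend carries the caveats on comparator and prior therapy. In this trial, Section 3.2.13 bars prior chemotherapy in newly diagnosed patients.

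The EKG arithmetic has limits. Section 2.1.2.1 calls the decline multi-exponential, and the calculation covers parent drug only. The more potent N-desmethyl metabolite has a half-life of 9 to 13 h; with a similar tmax (assumed) the same formula leaves 2^(−10.5/9) = 0.45 to 2^(−10.5/13) = 0.57 of its peak at 12 h. No relation between concentration and QTc is given. Inferring that a QTc effect would be missed is therefore unsupported; the arithmetic bears on comparability only.

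Magnesium has little bearing on dose escalation, because the DLT definition in Section 4.2 excludes correctable electrolyte abnormalities. The case for adding it rests on the toxicity profile.

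Finally, Section 6.2.1.1 puts left ventricular systolic dysfunction under 3%. At 3%, the maximum of 18 patients gives 18 × 0.03 = 0.54 expected cases, so even a scheduled repeat would not yield a useful frequency for events of that kind. This supports limiting the conclusion over adding a procedure.

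**Conclusion.** The point holds as a limitation of design and reporting. After screening, LVEF is observed only in patients selected by an event, so the trial cannot estimate how often it falls, and absent findings carry little information. The two scheduled steady-state EKGs lack the post-dose timing used on Day 1. A pre-dose tracing on twice-daily dosing would be at about 23% to 35% of peak parent drug, assuming one-phase decline and the protocol's tmax and half-life, so it may not be comparable with Day 1. A possibly related electrolyte disturbance has no scheduled measurement at any of 10 chemistry draws.

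The detection probabilities rest on assumed rates and show direction, not size. The gap does not invalidate the 3+3 dose decision. Nor do the documents support a reading that patients would be cleared for surgery on these data: Section 4.1.4 places surgery outside the protocol, and no section uses the cardiac results for that purpose.

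**What to change.** 1. In Section 10, footnote i, give the Day 8 and week 4 EKGs the 2 h post-AZD6244 timing already used on Day 1, and record the actual time from dose.
2. In Section 10, footnote a, add magnesium to the analytes, on the existing draws.
3. In Section 13.1, state that LVEF after baseline is measured only when a trigger event occurs, so the trial will report no frequency of LVEF decrease and will draw no cardiac safety conclusion from the absence of findings.

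No new visit or procedure is needed. The cost is one more analyte on samples already drawn, two visits arranged around the dose, and one added statement. Some incidental magnesium or EKG findings will need follow-up.
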